7.10 Long-Term-Safety-Visit (LTSV): Week 51 (21-day cycle) or Week 52 (28-day cycle)

Subjects on the 21-day cycle will return for the LTSV 21 days (± 2 days) after their last infusion of IMP, and subjects on the 28-day cycle will return for the LTSV 28 days (± 2 days) after their last infusion of IMP. The LTSV will be conducted prior to the administration of the subject's standard IgG treatment. The visit will consist of the following:

Adverse Event Assessment and Concomitant Medication Review

A review of adverse events, laboratory results and current medication will be performed. Current IgG treatment will be included under concomitant medication.

Subject Diary Review

The Subject Diary will be reviewed and collected as described in Section 6.2.

Vital Signs Pre-Infusion

Vital signs (body temperature, blood pressure, respiratory rate, and heart rate) will be recorded before the IMP infusion at the time intervals outlined in Section 6.3.

Physical Examination

The physical examination will focus on organs or systems that are known to be the target of complications in PIDD and the subject will be evaluated for infection as described in Section 6.4.

The subject's weight will be measured, and if the subject has gained or lost $\geq 5\%$ body weight since baseline, the amount of IgG for infusion must be adjusted accordingly per standard care.

Pre-Infusion Laboratory Assessments

The following laboratory samples will be obtained prior to administration of IMP/CP:

- Urine pregnancy test, if applicable (Section 6.5)
- Serum IgG trough levels will be measured prior to each Infusion of IMP (Section 6.6)
- Virology testing (Section 6.7), with a retention sample for future virology testing if necessary
- Retention blood sample for potential future virology testing (Section 6.7)
- Safety assessments, including general safety (hematology, blood chemistry, and urinalysis) (Section 6.8)

- Hemolysis assessment, including urine hemosiderin, serum haptoglobin, plasma free hemoglobin, Coombs test (direct anti-globulin test) (Section 6.9).
- For all subjects, a drop of ≥ 2.0 g/dL from the pre-infusion hemoglobin level or clinical signs of hemolysis between visits will lead to a full hemolysis work-up (Section 6.9).
- Antibodies to $\beta 2$ GPI and $\beta 2$ GPI-DI (Section 6.10) and retention sample.

7.11 Long-Term-Safety-Follow-up visit (LTSF) for subjects who are discontinued from IMP due to adverse events and if study is stopped

For subjects who are discontinued from study drug due to thrombotic or hemolytic events, and for all subjects if the study is stopped, subject will continue to be followed up and have the LTSF performed for 2 additional cycles (21-day cycle/28-day cycle) after LTSV, for a total approximate 3-month safety follow-up. The assessments will be conducted prior to the administration of the subject's standard IgG treatment.

For subjects who are discontinued from study drug due to anti- $\beta 2$ GPI immunogenicity, subject will continue to be followed up and have the LTSF performed after LTSV until immunogenicity titers are stabilized (or dropping) over 3 consecutive treatment cycles (21-day cycle/28-day cycle) after their last IMP infusion, and while on the subject's standard IgG treatment. The assessments will be conducted prior to the administration of the subject's standard IgG treatment. A follow-up phone call with the subject will take place approximately 8 weeks after the last LTSF performed for a review of laboratory assessments, including immunogenicity $\beta 2$ GPI and $\beta 2$ GPI-DI, adverse events and concomitant medication.

Adverse Event Assessment and Concomitant Medication Review

A review of adverse events, laboratory results and current medication will be performed. Current IgG treatment will be included under concomitant medication.

Subject Diary Review

The Subject Diary will be reviewed and collected as described in Section 6.2.

Vital Signs Pre-Infusion

Vital signs (body temperature, blood pressure, respiratory rate, and heart rate) will be recorded before the IMP infusion at the time intervals outlined in Section 6.3.

Physical Examination

The physical examination will focus on organs or systems that are known to be the target of complications in PIDD and the subject will be evaluated for infection as described in Section 6.4.

The subject's weight will be measured, and if the subject has gained or lost $\geq 5\%$ body weight since baseline, the amount of IgG for infusion must be adjusted accordingly per standard care.

Pre-Infusion Laboratory Assessments

The following laboratory samples will be obtained prior to administration of IMP/CP:

- Urine pregnancy test, if applicable (Section 6.5)
- Serum IgG trough levels will be measured prior to each Infusion of IMP (Section 6.6)
- Virology testing (Section 6.7), with a retention sample for future virology testing if necessary
- Safety assessments, including general safety (hematology, blood chemistry, and urinalysis) (Section 6.8)
- Hemolysis assessment, including urine hemosiderin, serum haptoglobin, plasma free hemoglobin, Coombs test (direct anti-globulin test) (Section 6.9).
- For all subjects, a drop of ≥ 2.0 g/dL from the pre-infusion hemoglobin level or clinical signs of hemolysis between visits will lead to a full hemolysis work-up (Section 6.9).
- Antibodies to $\beta 2$ GPI and $\beta 2$ GPI-DI (Section 6.10) and retention sample.

Follow-up Phone Call at 8 weeks after last LTSF

A follow-up phone call with the subject will take place approximately 8 weeks after the last LTSF performed for a review of laboratory assessments, including immunogenicity $\beta 2$ GPI and $\beta 2$ GPI-DI, adverse events and concomitant medication.

8 Administrative Considerations

8.1 Interim Analyses and Stopping Rules for Subjects on IMP

The DSMB (see Section 8.7), Sponsor, or PI may elect to terminate the study early as defined by the clinical study agreement.

The study may also be stopped, suspended, or terminated for subjects with specific characteristics or for all subjects at any or all sites for any of the reasons described below.

As described in Section 3.1 and Section 12.5, two interim analyses will be performed, based on the following in Group 1 and Group 2:

- Testing for antibodies to β -2 glycoprotein I ($\beta 2$ GPI) and to β -2 glycoprotein I domain I ($\beta 2$ GPI-DI);

[figure not shown]
- General safety laboratory tests (hematology, chemistry, urinalysis) before Infusion and on Day 7 after Infusion;
- Hemolysis laboratory test before Infusion and at Day 2 or 3 and Day 7 after Infusion;
- Clinical hemolysis & thrombosis assessment 1 h, 24 h and 72 h after Infusion;
- D-dimers & retention sample for proteins C & S 3-4 h after Infusion;
- Adverse Event data.

The algorithm for study-stopping rules shown in Figure 2 will be followed.

- If ≥ 2 subjects showing either (a) treatment-emergent positive anti- $\beta 2$ GPI and/or $\beta 2$ GPI- DI antibody titers ≥ 40 U as defined in Section 8.1.1 or (b) treatment-emergent positive anti- $\beta 2$ GPI and/or $\beta 2$ GPI-DI antibody titers > 20 U but < 40 U in combination with a treatment-emergent thrombotic or thromboembolic event, or a combination of (a) and (b).
- If ≥ 2 subjects present with confirmed thromboembolic events, as defined in Section 8.1.2, following full work-up for thrombosis.
- If ≥ 2 subjects present with confirmed hemolytic events, as defined in Section 8.1.3, following full work-up for hemolysis.

In the event any of the above occurs, administration of IMP for all subjects will be on hold until the investigator, DSMB, and FDA have reviewed the safety data and agree to resume dosing with IMP.

Figure 2. Summary of Stopping Rules

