6.10 Immunogenicity Testing

Immunogenicity testing for the detection of antibodies to $\beta 2$ GPI and $\beta 2$ GPI -DI will include the following tests:

- $\beta 2$ GPI Domain 1 QUANTA Flash Kit, INOVA Diagnostics
- $\beta 2$ GPI IgG Ab QUANTA Flash Kit, INOVA Diagnostics
- $\beta 2$ GPI IgM Ab QUANTA Flash Kit, INOVA Diagnostics

Blood samples for detection of antibodies to $\beta 2$ GPI and $\beta 2$ GPI -DI will be drawn at the following time points:

- **All subjects** at Screening
- **All subjects** before administration of IMP or CP at infusions 1 (baseline value), 2, 4, and 8, LTSV before infusion of the subject's standard immunoglobulin treatment

- Retention samples will be drawn at every visit for subjects on **IMP treatment**, from baseline through the LTSV

If any subject after receiving IMP seroconverts from negative to positive, with an elevated antibody titer at least 12 weeks apart, as defined in Section 8.1.1, then all prior retention samples for β 2GPI and/or β 2GPI-DI for all subjects should be analyzed.

6.11 3-4 Hour Post-infusion Safety Testing – Indicators of Thrombosis

For **all subjects**, blood samples will be drawn 3-4 hours after the end of IMP/CP infusion at Infusion 1, 2, 4, 8, 12 and 16.

Tests include:

- D-dimers
- Retention sample for protein C and protein S determination, in case d-dimer results indicate potential thrombosis or the PI determines a need for such testing from his evaluation (Note: a retention sample for protein C and protein S will also be taken at Screening to allow for a comparison of the subject's baseline status in the event of a later thrombotic episode or thromboembolic vascular event.)

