8.1.1 Immunogenic Reactions

Diagnosis of an immunogenic reaction that may lead to a thrombotic event will be based on treatment-emergent positive anti- β 2GPI and β 2GPI-DI antibody titers, defined as an antibody titer of ≥ 40 U found twice on tests that are at least 12 weeks apart and/or on treatment-emergent positive anti- β 2GPI and β 2GPI-DI antibody titers > 20 U but < 40 U in combination with a treatment-emergent thrombotic or thromboembolic event (Unlu et al., 2015) by these definitions will be considered significant events. If any subject after receiving IMP seroconverts from negative to positive, with an elevated rising antibody titer at least 12 weeks apart, then all prior retention samples for β 2GPI and/or β 2GPI-DI for all subjects should be analyzed.

Subjects who develop treatment-emergent anti- β 2GPI and/or β 2GPI-DI antibody titers > 20 U following exposure to IMP will be followed closely by the investigator for thrombotic and/or thromboembolic events. These subjects will have periodic (no more than 8 weeks apart) anti- β 2GPI and β 2GPI-DI antibody titer testing until they have completed 52 weeks of treatment with IMP or until immunogenicity titers have stabilized or are declining over 3 consecutive treatment cycles (21 or 28 day cycles), whichever is later.

As shown in Figure 2:

1. Any subject who has a significant event as defined above for anti- β 2GPI and/or β 2GPI-DI antibodies while being treated with IMP will permanently discontinue treatment with the IMP. The subject will remain in the study for safety assessments up to the time of the final follow-up phone call after LTSF (see Section 7.11).
2. The occurrence of two such significant events as defined above for anti- β 2GPI and/or β 2GPI-DI antibodies will be referred to the DSMB for an urgent ad-hoc review to determine if this qualifies as a potential study-stopping event as defined above.

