8.1.2 Thrombotic Events

As shown in Figure 2:

- Investigator will examine subjects for clinical signs of thrombosis (Section 6.12.2). Positive assessments will lead to a full work-up for thrombosis, as appropriate, according to the facility's standard of care. In the case that d-dimer results indicate potential thrombosis, protein C and protein S testing will be done based on Investigator evaluation (Section 6.11).
- Any subject who is diagnosed with a thromboembolic event based on clinical and laboratory assessment while being treated with IMP will permanently discontinue treatment with the IMP and will receive standard medical care. The subject will remain in the study for safety assessments up to the time of the final follow-up phone call after LTSF (see Section 7.11). All such events will be referred to the DSMB for an urgent ad-hoc review to determine if this event qualifies as a potential study-stopping event as defined above.
- Any subject who is diagnosed with a thrombotic or thromboembolic vascular event based on clinical and laboratory assessment while being treated with the commercial product will receive standard medical care and continuation in the study will be at the discretion of the Investigator. If the subject is terminated from the study, the PI will determine continued treatment for managing the disease, in consultation with the subject's treating physician and per standards of care. The subject will remain in the study for safety assessments up to the time of the final follow-up phone call after LTSF (see Section 7.11).
- If two or more subjects experience confirmed thrombotic or thromboembolic vascular events in the trial as a whole in subjects receiving IMP, the DSMB will put the study on temporary hold while an assessment is made. All treatments with the IMP will be discontinued until the investigator, the DSMB, and the FDA have reviewed safety data for subjects enrolled. During this time, no new subjects will be enrolled. If a subject should require a scheduled infusion during this time, they will continue therapy with a commercially available preparation (CP). IMP infusions will be recommenced if approval to continue the study is given by the DSMB and FDA.

The IRB/IEC and the US FDA/appropriate regulatory authority for trials outside the US will be immediately notified of any suspected ADRs involving thromboembolic events.

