8.7 Data Safety Monitoring Board (DSMB)

In addition to the Sponsor and PI’s responsibility for oversight, study oversight will be under the direction of an independent DSMB. The DSMB will be responsible for ongoing review of safety data. The PI will assess seriousness, causality, and intensity (severity) of an adverse event.

The processes, composition, and intervals of meetings will be described in detail in a separate DSMB charter written in accordance with the FDA *Guidance* [March, 2006].

The DSMB will include members with expertise in immunology and experience in clinical trials with immunoglobulin product. The DSMB will at minimum meet after all subjects in Group 1 have received their first infusion of IMP and the immunogenicity results are available, prior to Infusion 2. They will meet again once a further 10 subjects have received their first infusion of IMP and immunogenicity results are available prior to Infusion 2. These subjects will continue on IMP during review of safety data, but no further subjects will receive IMP until DSMB and FDA provide safety evaluation. At any time a thrombotic or hemolytic event is suspected or reported the DSMB will review the data of individual subjects and if needed additional subjects to make a determination.

All immunogenicity data except for the screening data, baseline and Infusion 2 (prior to infusion) will be batch tested. The DSMB can request that the retention samples for immunogenicity testing (anti-β2GPI and β2GPI-DI antibodies) or Protein C and S can be tested at any time. Once Group 1 and Group 2 have been approved, a DSMB meeting will take place after 20 subjects in Group 3 receive at least 6 doses of IMP. In the event any safety concerns are raised in the periods between meetings by SAEs, the DSMB Chair will hold ad hoc meetings to ensure the safety of all subjects and determine whether the concern warrants applying the stopping rules.

The DSMB will provide its analysis and conclusions to ProMetic BioTherapeutics, to the IRBs, and to the FDA. The DSMB Charter is a separate document detailing the composition, governance, meeting preparation and conduct, voting rules and stopping rules.

9 Concomitant and Prohibited Medications

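### A thrombotic event with a single titer of 40 U or more does not count toward the automatic immunogenicity hold, although the same event with a titer between 20 and 40 U does

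*Protocol*

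**What the plan says.** Protocol 8.1 sets three automatic holds, each triggered by two or more subjects: immunogenicity, confirmed thromboembolic events, and confirmed hemolytic events. IMP then stops for everyone until the investigator, DSMB and FDA agree to resume.

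The immunogenicity hold has two arms, and the two subjects may qualify by different arms.

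- Arm (a) concerns "antibody titers ≥ 40 U as defined in Section 8.1.1 or (b) treatment-emergent positive" titers under arm (b). The definition in 8.1.1 requires the value of 40 U or more to be "found twice on tests that are at least 12 weeks apart".
- Arm (b) takes titers above "20 U but < 40 U in combination with a treatment-emergent thrombotic or thromboembolic event, or a combination of (a) and (b". Section 8.1.1 repeats the upper limit when it defines a significant event: "titers > 20 U but < 40 U in combination with a treatment-emergent thrombotic or thromboembolic event".

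The surrounding provisions matter for the size of the problem.

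- Under 8.1.2, any subject with a thromboembolic event on IMP stops IMP permanently. "All such events will be referred to the DSMB for an urgent ad-hoc review".
- Under 6.10, titers are scheduled before Infusions 2, 4 and 8 and at the LTSV. "Retention samples will be drawn at every visit for subjects on" IMP treatment.
- Under 8.7, "All immunogenicity data except for the screening data, baseline and Infusion 2 (prior to infusion) will be batch tested", although the DSMB may ask for retention samples to be tested at any time.
- Under 8.1.1, subjects above 20 U are retested at intervals of no more than 8 weeks.
- Under 7.11, subjects discontinued for thrombosis have the "LTSF performed for 2 additional cycles (21-day cycle/28-day cycle) after LTSV".

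The SAP does not restate or alter the stopping rule.

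**The concern.** The two arms would cover every titer above 20 U in a subject with an event only if any value of 40 U or more satisfied arm (a). The 12-week repeat prevents that. With the same event, moving an unconfirmed titer from 39 U to 40 U takes the subject out of the count, so the stronger antibody signal gives less protection. Nothing in either document explains why a higher titer should be treated more leniently.

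What is at stake is the automatic hold for the other subjects. When the second qualifying subject has confirmed titers of 40 U or more without an event, IMP dosing of everyone else continues by default unless the DSMB chooses to act.

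**Working it through.** **Inputs.** The arms and the two-subject trigger come from Protocol 8.1. The 12-week confirmation comes from 8.1.1, the separate thromboembolic hold from 8.1 and 8.1.2, the visit weeks from Table 4, and the follow-up visits from 7.10 and 7.11. There is no published figure to reproduce, because the rule has no stated operating characteristics.

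**One subject with a thrombotic event, rule as written**

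| Titer state | Arm (a) | Arm (b) | Counts? |
|---|---|---|---|
| 20 U or less | no | no | no |
| above 20 U, below 40 U | no | yes | yes |
| 40 U or more, unconfirmed | no | no | **no** |
| 40 U or more, twice at least 12 weeks apart | yes | – | yes |

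Without an event, only the last row counts.

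**Two subjects.** Four titer states, each with or without an event, give 8 subject types. Unordered pairs, allowing two of the same type: 8 × 9 / 2 = 36.

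- Thromboembolic hold: 4 types have an event, so 4 × 5 / 2 = 10 pairs.
- Immunogenicity hold as written: 3 types count, so 3 × 4 / 2 = 6 pairs. Two of those types have an event, so 2 × 3 / 2 = 3 pairs are already among the 10.
- Total as written: 10 + 6 − 3 = 13.
- Without the upper limit: 4 types count, giving 4 × 5 / 2 = 10 pairs. Three of those types have an event, so the overlap is 3 × 4 / 2 = 6. Total: 10 + 10 − 6 = 14.

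Four pairs newly meet the immunogenicity rule, but in three of them both subjects had an event and the thromboembolic hold already applies. The one changed decision is an unconfirmed titer of 40 U or more with an event, paired with confirmed titers of 40 U or more without an event.

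**Example.** Subject A has 35 U and an event; Subject B has two titers of 40 U or more 12 weeks apart and no event. The immunogenicity count is 2, so dosing is held. Change A to a single 45 U: immunogenicity count 1, thromboembolic count 1, no automatic hold.

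**When arm (a) can first be met.** The first planned sample after IMP is at week 3 (21-day cycle) or week 4 (28-day cycle). Using retention samples from every visit, the earliest confirmation is 3 + 12 = week 15 or 4 + 12 = week 16. On the scheduled tests alone (weeks 3, 9, 21, 51 or 4, 12, 28, 52) it is week 21 or week 28.

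**Follow-up after a thrombotic discontinuation.** The LTSV and two LTSF visits fall 3, 6 and 9 weeks after the last infusion on the 21-day cycle, and 4, 8 and 12 weeks on the 28-day cycle. On the 21-day cycle they end at 63 days against the 84 required, so they cannot by themselves confirm a titer first found at the last infusion.

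**Exposure of others.** If A's first titer of 40 U or more is drawn at about the time of the event, arm (a) completes the count no earlier than 12 weeks later. Each other subject is due 12 / 3 = 4 or 12 / 4 = 3 infusions in that time. With about 75 enrolled and 73 others, the ceiling is 73 × 3 = 219 to 73 × 4 = 292 infusions. This assumes that all 73 are on IMP and that the DSMB does not act.

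**Could the pairing arise?** Protocol 1.4 dates the DSMB's approval after Group 1 to 26 May 2016 and FDA's clearance of Group 3 to 20 December 2016, 208 days or 208 / 7 = 29.7 weeks later. A Group 1 subject still on IMP could by then have met arm (a), while about 60 Group 3 subjects were starting unstaggered.

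**The case against.** The strongest reply is that other provisions already deal with the missed pairing. Every thromboembolic event goes to urgent DSMB review whatever the titer. Section 8.7 lets the board look at additional subjects, so it could consider A and B together, and regulators are told at once of suspected thromboembolic reactions. A's event triggers testing of A's stored samples, and B's seroconversion can require stored samples from all subjects to be analyzed. With three assays and a sample at every visit, any treatment-emergent value between 20 and 40 U brings A into arm (b). Titers no more than 8 weeks apart mean that confirmation need not depend on the LTSV and LTSF visits. The 36 pairs are not weighted by likelihood, and the infusion count is a ceiling that staggered starts would lower. Figure 2 and the DSMB Charter were not available and might word the rule differently.

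Most of this stands as a limit on the impact. It does not repair the rule. DSMB review is discretionary, whereas the protocol chose a mandatory hold that needs FDA agreement to lift. Stored samples and repeat titers help only if they yield a value between 20 and 40 U or a second high value at least 12 weeks from the first. Sections 8.1 and 8.1.1 agree on the upper limit, so an unseen figure or charter cannot be assumed to override them.

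**Conclusion.** The rule is wrong as written: an unconfirmed titer of 40 U or more with a thrombotic event counts under neither arm, while a lower titer with the same event counts. The practical effect is small. It changes the automatic decision in 1 of 36 pairings of subject types, and the affected subject is off IMP and under urgent DSMB review in any case. The conclusion assumes that the subject has no other treatment-emergent value between 20 and 40 U and no qualifying repeat, and that Figure 2 and the Charter follow the text. The probability of the pairing cannot be derived from the documents. The point does not touch the primary endpoint, the error rate or the power.

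**What to change.** In arm (b) of Protocol 8.1 and in the matching definition in 8.1.1, remove the upper limit of 40 U. Any treatment-emergent titer above 20 U together with a treatment-emergent thrombotic or thromboembolic event then counts as a significant event. Leave arm (a) as it is. Check Figure 2 and the DSMB Charter and align them if they repeat the limit.

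The cost is an amendment to two sections, with the regulatory submission and IRB/IEC approval described in 16.4. No new samples or data are needed. The hold becomes slightly easier to trigger, by the one pairing identified above.
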